#### 9. STATISTICAL CONSIDERATIONS

## 9.1 General Design Issues

This randomized controlled trial is a single-site pilot trial to assist in feasibility assessment and sample size estimation in a pivotal trial to test the hypothesis that listening to a Comfort Talk® app with calmative content reduces pain, anxiety, and post-procedural medication use. The study design is based on a 1:1 randomized attribution of participants to an app or white noise as control condition.

The feasibility criteria are not hypothesis driven and are based on practical pass/fail criteria:

primary feasibility outcome parameter:

• ability to obtain complete on-site data sets from at least 90% of patients enrolled - with at least 40% from patients in the app group and at least 40% from patients in the control group)

secondary feasibility outcome parameters:

- ability to enroll 60 patients by day 150 after initiation of recruitment in the clinic (=day 1)
- obtaining 38 packages of filled out diary cards (at least 16 from patients in the app group and at least 16 from patients in the control group).
- 90% of patients in app group listen to app  $\geq$ 5 min

Since a significant reduction in anxiety in the waiting room is the main ingredient that underlies all other hypothesized effects for Phase II outcomes, even in the face of proven technical feasibility of trial execution, it was chosen as the overall primary objective for Phase II.

Statistical hypotheses for Phase II are:

Providing participants a calmative Comfort Talk® app at the time of their dental outpatient visit

- reduces anxiety in the dental waiting room (primary hypothesis)
- reduces pain in the dental waiting room
- reduces anxiety during dental treatment
- reduces pain during dental treatment
- improves patient satisfaction with the dental visit
- reduces anxiety in the week after treatment
- reduces pain in the week after treatment
- reduces need for opioids and analgesics the week after treatment

The overall premise is that showing patients at the time they experience distress how to cope while they are still under physician/dentist supervision will carry over into recovery and thus reduce need for addictive drugs (see also 2.2).

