Using this number of 66 patients as guide to determine a target study size for assessment of the feasibility parameters an enrollment of 72 patients seemed compatible with an early drop-out of 6 patients resulting in an expected 91.7% onsite data return rate. This will also support the expectation of receiving 38 packages of filled out diary cards (53%), a secondary objective. In a prior breast biopsy trial, in which patients collected for 5 days 4 daily salivary cortisol samples, filled out more extensive diary cards, and sent all back to the lab, 36% complied (45). Considering the higher burden of also getting 4 daily salivary samples and 4 daily entries as compared to one daily entry on cards at bed-time a 53% return rate for this pilot is reasonable.

This sample size of 72 participants may also give an estimate in as far results previously achieved with live delivery of Comfort Talk® may be transferable to assumptions for app delivered Comfort Talk® content.

The following sample size estimate supports the evaluation of post-procedure pain and is based on a prior breast biopsy trial (19) during which we collected postoperative pain measures. In that study, postoperative pain ratings in the live Comfort Talk group were less than those of the control group (1.6 vs 3.5) with a standard deviation of 2.0. Assuming a similar reduction in pain from 3.5 to 1.6 on day 1 (similar effect size in a study by from TUSDM) (43) and a standard deviation of 2.0, 38 subjects total would be needed for a two-sided test with a power of 0.80 and an alpha of 0.05. Considering that not everyone will send back their diaries, the target of 72 patients may suffice.

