If the data does not meet the assumptions required for the time-series analysis methods listed above, the time-series data from each patient will be summarized by calculating area under the curve using trapezoidal rule. Normality will be assessed graphically using histograms and q-q plots. Area under the curve will be compared between the two treatment groups using t-test if normally distributed or if normality can be achieved by log-transformation. Mann-Whitney U test will be used if data is non-normal.

Pain and anxiety for the week after the post procedure will be assessed for linearity graphically. Individual patient pain and anxiety slopes will be compared using t-test or Mann-Whitney U test, as appropriate, to determine if the rate of change of pain and anxiety is different between treatment and control groups. In addition, the overall mean pain and mean anxiety for each patient will be calculated and compared between treatment and control groups using t-test or Mann-Whitney U test as appropriate.

Drug usage, converted in equivalence drug score, and satisfaction scores will be assessed by t-test if normally distributed or Mann-Whitney-U test if non-normal.

All tests will be two-sided at a significance level of <0.05. Sample size will be based on results of Phase I assuming a power of 80%. SAS version 9.4 will be used for analysis.

Patients' age, gender, procedure type, and NIDA Quick score will be assessed for their potential as confounding factors. This will support guidance for trial design in Phase II.

The study sample of this pilot is likely underpowered to perform meaningful subanalyses of differences in intervention effect between gender and racial/ethnic subgroups. They will be performed to not miss potentially clinically significant differences as prescribed by NIH policy.

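### Section 9.6 plans two unranked week-after tests, slopes and weekly means, that can point in opposite directions, and names neither as the test of the hypotheses about level

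*Combined protocol and SAP*

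**What the plan says.** Section 9.1 lists, among the hypotheses for Phase II, that the app "reduces pain in the week after treatment", with a matching hypothesis for anxiety. Both are statements about level.

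Section 9.2 supports the evaluation of post-procedure pain with a level contrast at one time point: "Assuming a similar reduction in pain from 3.5 to 1.6 on day 1". With a standard deviation of 2.0 it concludes that "38 subjects total would be needed for a two-sided test with a power of 0.80 and an alpha of 0.05". The same number, 38 of 72, is the diary-return target.

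Section 9.6 sets out the week-after analysis. Linearity is judged from graphs. Then "Individual patient pain and anxiety slopes will be compared using t-test or Mann-Whitney U test, as appropriate", with the stated purpose of seeing whether the rate of change differs between arms. The next sentence adds a between-arm comparison of each patient's overall mean pain and mean anxiety, by the same two tests. Further on, "All tests will be two-sided at a significance level of <0.05". The section does not say which comparison answers the section 9.1 hypotheses, how to read a difference in slopes, or what to conclude if the two disagree. It also says that the analysis plan may change with the data found in this pilot.

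**The concern.** A slope removes the level, and the level is what the hypotheses are about. On a 0–10 scale, an arm that starts at 1.6 has less room to fall than one that starts at 3.5. If both arms settle at a similar value by the end of the week, the arm with the early benefit has the flatter line, and a slope comparison reads as slower improvement. If the benefit is the same every day, the lines are parallel and the slopes carry no information about it.

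The weekly-mean comparison does address level, but the plan gives it no priority over the slope. A blinded analysis that follows the text could report a significant slope difference against the app next to a non-significant mean difference, with no rule for choosing. The pilot is meant to guide the sample size and analysis of Phase II, so such a result could misdirect the handling of the week-after outcomes there.

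**Working it through.** **Inputs from the documents.** Day-1 pain 3.5 vs 1.6, SD 2.0, two-sided 0.05, power 0.80, 38 diaries (section 9.2). Allocation is 1:1 (section 9.1), taken as 19 diaries per arm. There are seven daily entries (section 6.2.5).

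**Assumptions, because the documents give no figure.** Straight-line courses over days 1–7. Between-patient SD 1.5 and residual SD 1.3, so the total SD is √(2.25 + 1.69) = 1.98, in line with the plan's 2.0. Between-patient SD of true slopes 0.1 to 0.3 points per day.

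**1. The plan's own figure.** Normal approximation: n per arm = 2 × (1.960 + 0.842)² × 2.0² / 1.9² = 17.4, so 18 per arm and 36 in total. The exact two-sample t calculation gives 18.4, so 19 per arm and 38 in total, with power 0.813. The stated 38 is reproduced. It is the size for a day-1 contrast, which neither week-after comparison tests directly.

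**2. What each comparison sees.** Differences are app minus control.

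| Course, day 1 to day 7 | Control slope | App slope | Slope difference | Mean difference |
|---|---|---|---|---|
| Both reach 1.0 | (1.0−3.5)/6 = −0.417 | (1.0−1.6)/6 = −0.100 | +0.317 | 1.30−2.25 = −0.95 |
| Both fall to 40% of day 1 (1.40; 0.64) | −0.350 | −0.160 | +0.190 | 1.12−2.45 = −1.33 |
| Constant 1.9-point gap | equal | equal | 0 | −1.90 |
| Equal on day 1, gap of 1.9 by day 7 | – | – | −1.9/6 = −0.317 | −0.95 |

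**3. Slope test.** For days 1–7 the sum of squared deviations is 28. The variance of one patient's fitted slope is τ² + 1.69/28 = τ² + 0.0604, where τ is the SD of true slopes. The SE of the arm difference is √(2 × variance / 19), which is 0.086 at τ = 0.1 and 0.126 at τ = 0.3.
- Converging to 1.0: 0.317/0.086 = 3.7 and 0.317/0.126 = 2.5. On 36 degrees of freedom this gives significance against the app in about 95% and 69% of trials. Simulation gives about 70–96%.
- Falling to 40% of day 1: 0.190/0.086 = 2.2 and 0.190/0.126 = 1.5, or about 57% and 31%. Simulation gives about 33–70%, the higher values arising when ratings are limited to 0–10.
- Constant gap: about 5% in total, split between the two directions.
- Growing benefit: significant in the app's favour in about 64–95% of simulated trials.

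**4. Weekly-mean test.** The variance of one patient's mean is 2.25 + 1.69/7 = 2.49, so the SE of the difference is √(2 × 2.49 / 19) = 0.512.
- Constant 1.9 points: 1.9/0.512 = 3.7, power about 94–95%.
- Converging to 1.0: 0.95/0.512 = 1.9, power about 45%.

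**5. Both together.** In the converging case the adverse slope is the only significant week-after result in about 35–53% of simulated trials.

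**6. Sensitivity.** With total SD 2.0, equal correlation between days of 0.3, 0.5 or 0.7 and no variation in true slopes, the converging case gives an adverse slope in 85%, 95% and 99.6% of runs and a favourable mean in 39–61%. For a constant 1.9-point gap the mean test has 91–99% power. Limiting scores to 0–10 then tilts the slope test against the app, with adverse significance in about 9–17% of runs under a constant benefit of 1.0 or 1.9 points. The correlation changes these rates but not the sign of the slope difference.

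**The case against.** A reader might infer that the plan cannot see a constant benefit at all, or that an app that works will look worse than control. The documents support neither.

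- **The weekly mean is already planned.** The sentence after the slope comparison tests it, and it has about 94% power for a constant 1.9-point gap. Descriptive statistics by time point and arm, and plots of each patient's ratings over time, are also planned, so a lower day-1 level would be visible.
- **The slope has its own stated question.** Section 9.6 presents it as a comparison of rates of change. Nothing there says that a flatter slope means a failed app.
- **The wrong sign needs an early gap that narrows.** The 3.5 vs 1.6 figures come from a breast-biopsy trial with live delivery. Nothing states how pain moves over a week in this clinic. App patients may use the app at home during the diary week, and section 9.1 expects coping to carry over into recovery, so a sustained or growing benefit is also consistent with the plan. A growing benefit shows up on the slope in the app's favour.
- **Unequal diaries matter less than the extreme case suggests.** Three consecutive days give a slope error factor of 1/2 against 1/28 for seven days, a ratio of 14. Days 1, 4 and 7 give 1/18, a ratio of 1.6. Including variation in true slopes brings the consecutive-day ratio to about 12 (0.855/0.070 at τ = 0.1) or 6 (0.935/0.150 at τ = 0.3). No rate of partial diaries is given.
- **The stakes are limited.** These outcomes are secondary, the Phase II primary outcome is already fixed as waiting-room anxiety, and the plan is provisional.

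All of this stands, and it narrows the point. It does not supply a ranking between the two comparisons, a rule for a conflict, or a direct test of the day-1 contrast.

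**Conclusion.** The point holds in this form: the plan has two unranked week-after comparisons, only one of which measures what the hypotheses state. The slope comparison says nothing about a constant benefit, tends to be significant against the app if an early benefit narrows (about 70–96% or 33–70% of simulated trials for the two courses examined), and favours the app if the benefit grows. Its sign therefore cannot be read as benefit or harm. The weekly mean handles a constant benefit well, but reaches significance in only about 45% of trials in the converging case, so the adverse slope can stand alone.

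The signs in the table follow by arithmetic from each assumed course. The percentages also rest on 19 complete diaries per arm and the assumed variances. This is a cheap improvement of low severity: secondary outcomes, a feasibility pilot and an analysis plan that is open to change.

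**What to change.** In section 9.6, name the between-arm difference in mean rating over days 1–7 as the test of the week-after pain and anxiety hypotheses. For pain, state the day-1 difference as the contrast behind the 38-diary figure. Adjust for the pre-tablet rating, which is already collected.

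One way is a mixed model of the daily ratings in SAS with arm, day, arm by day and the pre-tablet rating as fixed effects and a random intercept and slope. Both contrasts come from the same fit, and patients with different numbers of diary days are weighted accordingly. The arm-by-day term estimates the same slope difference, so it too should be descriptive. The essential change is the ranking; the model is a convenience.

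Report individual slopes as plots and summaries, and state that they are not evidence of benefit or harm.

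The cost is SAP wording, a little more modelling work and the loss of the formal slope test. No new data are needed, and SAS is already the planned software.

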#### 9.5 Outcomes

The outcomes are based on patient's reported measures of anxiety, pain, satisfaction rating on a Likert scale, and medication use and objective numbers with regard to the feasibility measures. These data are clear numerical values and not subject to interpretation/adjudication with regard to their reported value.

There will be no loss of follow-up for data for the primary outcome parameter since all patients who are on site are the denominator and any missing data would be reflected in the percentage of complete on-site data sets.

For management of any subsequent missing intermittent data the method will use all data available data that are available within the intent-to-treat overall approach.

We will be using all available data and calculate the percent missing data for each treatment group. The degree of missingness will inform accept/reject feasibility which is defined as complete on-site data sets from at least 90% of patients enrolled with at least 40% from patients in the app group and at least 40% from patients in the control group) and 38 packages of filled out diary cards 52% with at least 16 (22%) from patients in the app group and at least 16 from patients in the control group (22%)

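### Weekly diary means and slopes give a 2- or 3-card diary the same weight as a full one, which costs slope precision and can bias the means if completion or time course differs by arm

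*Combined protocol and SAP*

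**What the plan says.** Patients make one diary entry per day for 7 days. For that week, section 9.6 (Data Analyses) plans two per-patient summaries. The first is a rate of change: "Individual patient pain and anxiety slopes will be compared using t-test or Mann-Whitney U test". The second is a level: "the overall mean pain and mean anxiety for each patient will be calculated and compared between treatment and control groups", again by t-test or Mann-Whitney as appropriate.

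The only rule for gaps is in section 9.5 (Outcomes): "For management of any subsequent missing intermittent data the method will use all data available data that are available". The same section has the percentage of missing data reported per arm. Sections 4.2 and 8 keep the data of withdrawn patients. No section sets a minimum number of cards, a weight for short diaries or an adjustment for day, and a filled-out diary package is not defined by a number of cards.

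The repeated-measures and ordinal models in section 9.6 are described for the 10-minute chair-time ratings; no such model is named for the diary week. Drug use is an outcome over one week, converted to an equivalence score. The text does not say whether that score is a sum or a daily average, or what a missing day contributes.

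**The concern.** This point is about diaries that come back partly filled. Pain and anxiety may change over the days after a visit, so a mean over days 1-3 and a mean over days 1-7 estimate different quantities. A slope fitted to two or three points is far noisier than one fitted to seven. The plan nevertheless enters each as one observation per patient.

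Partial diaries are foreseeable. Section 9.2 expects 38 packages from 72 patients (53%) and cites 36% compliance in an earlier, more burdensome diary study. The arms also face different incentives: app patients get their download coupon at the visit, controls only after returning the diary. Different completion by arm is therefore plausible, though its direction and size are unknown.

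At stake are the diary comparisons and what is carried into Phase II, since section 9.6 bases the later sample size on Phase I results.

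**Working it through.** **1. The plan's own figure.** Section 9.2 supports the diary pain comparison thus: "Assuming a similar reduction in pain from 3.5 to 1.6 on day 1" "and a standard deviation of 2.0, 38 subjects total would be needed". Inputs: difference 3.5 − 1.6 = 1.9, SD 2.0, standardised effect 1.9/2.0 = 0.95, two-sided 0.05, power 0.80, 1:1 allocation. The two-sample t-test needs 18.4, so 19 per arm and 38 in total (power 0.813 at 19 per arm). The figure reproduces. It sizes day-1 pain, not the weekly mean or slope.

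**2. Slope precision.** For k cards from day 1 onward, the error variance of a patient's least-squares slope is σ²/Sxx, where Sxx is the sum of squared deviations of the days from their mean.

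| Cards | Sxx | Error variance relative to 7 cards (28/Sxx) |
|---|---|---|
| 7 | 28 | 1 |
| 6 | 17.5 | 1.6 |
| 5 | 10 | 2.8 |
| 4 | 5 | 5.6 |
| 3 | 2 | 14 |
| 2 | 0.5 | 56 |

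One card gives no slope.

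**3. Effect on the slope test.** Assumed, because the documents give no values: 19 returners per arm, within-patient SD 1.0, between-patient slope SD 0.15, true slopes −0.25 and −0.50 per day. The variance of an observed slope is 0.15² + 1.0² × (average of 1/Sxx).

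- All 7 cards: 0.0225 + 0.0357 = 0.058.
- 30% of diaries with 4-5 cards: 0.0225 + 0.7 × 0.0357 + 0.3 × (0.2 + 0.1)/2 = 0.093.
- 30% of diaries with 2-3 cards: 0.0225 + 0.7 × 0.0357 + 0.3 × (2 + 0.5)/2 = 0.42.

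Simulated t-test power is 0.87, 0.69 and 0.25 respectively. With equal slopes, the false-positive rate stayed at about 0.04-0.05 in the scenarios simulated, and the estimated slope difference is unbiased. A Phase II sample size built on a diary slope would inflate by 0.093/0.058 = 1.6 to 0.42/0.058 = about 7 times.

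**4. Weekly means.** Assume a linear fall from 3.5 (the plan's control figure) on day 1 to 1.0 on day 7: 2.5/6 = 0.417 per day. The mean over days 1-7 is 2.25, and over days 1-3 it is 3.08. Stopping after 2, 3 or 4 cards moves the centre of the recorded days from day 4 by 2.5, 2.0 or 1.5 days. The mean shifts by 1.04, 0.83 or 0.63, on average 0.83.

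- Different completion: if 10% of control and 40% of app returners stop after 2-4 cards, the spurious difference is 0.83 × (0.40 − 0.10) = 0.25 point, with the app arm looking worse.
- Range: for 3-card diaries the bias is 2 × daily slope × difference in share. This is 0.02 to 0.32 point for slopes of 0.1-0.4 per day and share differences of 10-40 percentage points.
- Different time course: with slopes −0.25 and −0.50 and 30% of diaries at 2-3 cards in both arms, the simulated mean difference shrinks from −0.77 to −0.58.
- Equal completion and equal time course: simulated difference −0.007, that is, no bias.

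**5. Drug score.** If it were summed over filled cards and use were steady, 3 of 7 cards would capture 3/7 = 43% of the week. A raw average per recorded day is not a safe alternative. If use fell from 1.5 to 0.3 units per day (assumed), the daily slope is 0.2, and diaries stopping at 2-4 cards average 2 × 0.2 = 0.4 too high. With the 10% versus 40% split this gives 0.4 × 0.30 = 0.12 units per day, or 13% of the weekly mean of 0.9, with no effect.

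**The case against.** Four points count against the concern, and each stands in part.

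- **The rank test is available.** Mixing 2-card and 7-card slopes gives heavy tails, where the plan would turn to Mann-Whitney. With within-patient SD 1.3, the same slopes as above and 30% of diaries at 2-4 cards, power is 0.40 by Mann-Whitney and 0.23 by t-test. The rank test removes the domination by extreme slopes, but its power with full diaries is 0.71, so a real loss remains.
- **Mildly incomplete diaries do little harm.** In that setting, 30% of diaries at 5-6 cards lowers t-test power only from 0.75 to 0.64. The severe losses need diaries of two to four cards.
- **The bias is modest and would be visible.** A shift of 0.25 point is under half the standard error of the mean difference at 19 per arm (about 0.56), and the false-positive rate rises only to about 0.07. Section 9.6 also plans descriptive statistics by time point and arm, and section 9.5 reports missingness by arm. These would reveal the problem but not correct the planned tests.
- **The plan is provisional.** Section 9.6 allows the approach to change once Phase I shows the distribution and time course, and these are secondary outcomes of a pilot. That limits the consequence and makes correction easy.

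Two stronger readings are tempting. A reader might infer that missing days are counted as days without drugs. The documents do not say so: the construction of the score is left open, and zero-counting would follow only if it were a sum over filled cards. A reader might also infer that the weekly means are biased as such. They are not; that needs a trend over the week together with completion or time courses that differ by arm.

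**Conclusion.** The concern holds as a weakness of the planned summaries. Section 9.6 compares unweighted per-patient slopes and means, and section 9.5 lets any number of cards enter. The 14-fold and 56-fold variance ratios for 3 and 2 consecutive cards are arithmetic and need no assumption beyond equal, independent daily errors. The slope test loses power but stays valid. Bias in the means is conditional, and the 0.25-point figure is an illustration. For drug use the fault is an unspecified rule, not a wrong one.

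Every share of partial diaries, the daily trends and the within-patient SDs are assumptions, because the documents give none. The primary outcome, completeness of on-site data, does not depend on any of this, nor do the other feasibility criteria. The change should be made before diary data are analysed; it does not threaten the pilot's main conclusion.

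**What to change.** Extend the repeated-measures approach of section 9.6 from chair time to diary days 1-7:

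- For each diary outcome, fit a mixed model with arm, categorical day and arm-by-day, using every returned card. Let patients differ in slope, through a random intercept and slope or an unstructured covariance. The latter has 7 × 8/2 = 28 parameters, heavy for about 38 diaries.
- Report two contrasts: the arm difference averaged over days 1-7, and the arm difference in linear trend. The second keeps the planned rate-of-change comparison.
- If scores are strongly skewed, use the ordinal repeated-measures model already named in section 9.6.
- Analyse drug use by day with adjustment for day, not as a sum or raw average over available cards, and state how a missing day is treated.
- If a diary slope is used to size Phase II, take its variance from the model, not from the spread of per-patient slopes.

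The cost is a paragraph of analysis-plan text and slightly more SAS programming. The model relies on missingness being explained by the observed data. That should be stated, but it is a weaker assumption than the unweighted comparison of means needs.

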#### Sample Size and Population

The pilot will be conducted in the Craniofacial Pain Center of TUSDM. Patients included in the trial will be those who come for the procedures offered in the Craniofacial Pain Center such as fitting and adjusting dental bite appliances, fitting and adjusting oral appliances for management of sleep apnea, trigger point therapy, botulinum toxin therapy, and various craniofacial and cervical nerve blocks for pain management. Procedures last on the average 45 min.

Subjects will be randomized to one of four tablets using a randomization plan generated by SAS version 9.4 PROC PLAN. Given that four tablets will be available at one time, four subjects will be randomized per block. Given a total sample size of 72, subjects will be randomized to 18 blocks.

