## 9.2 Sample Size and Randomization

The goal is to enroll 72 patients in a randomized design with 36 patients utilizing the app and 36 patients not utilizing the app. Those randomized to utilizing the app (app group) will receive a tablet with the app, those randomized to not utilizing the app (control group) will receive a tablet with white noise.

Based on prior trial experience, it is likely that 90% of patients on site will provide onsite data sets (primary objective). In two prior trials, in which 241 and 201 patients, respectively, were followed through their invasive medical procedures, all enrolled patients (100%) provided these data (1,3). In a breast-biopsy trial, 4 of 240 (1.6%) withdrew by that stage (2). In these past trials patients received more personal attention through live delivery of the content that is now offered in an app, and thus willingness to remain in the study may not be as high in the current trial but still should exceed 90% for feasibility. To arrive at a reasonable sample size to satisfy this requirement, but also obtain a sense of validity of the primary hypothesis for Phase II and obtain estimates of data distribution, which will be critical for sample size and analysis planning Phase II, we conducted following sample size calculations.

Assuming an average anxiety rating of 4 at the end of the waiting room time without prior guidance in relaxation or app (see Fig 3., time 0), the expectation of improved subsequent outcomes with a 35% reduction in anxiety to 2.6 based on Schupp et al (33 vs 53 on STAI - (1) and a standard deviation of 2, 66 patients would be needed for a two-sided test with a power of 0.80 and an alpha of 0.05.

This degree of reduction in anxiety is clinically significant based on prior work in a clinical trial that demonstrated that a 35% difference in anxiety at the onset of an invasive medical procedure is associated with significant differences in the subsequent experience of pain and anxiety during the procedure, need for opioid analgesics and sedatives, and the overall length of the procedure. These factors directly affect procedure safety and throughput (e.g. economical efficiency).

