## 9.6 Data Analyses

All outcome parameters for assessment of study feasibility are pass/fail criteria not requiring further analyses beyond calculations of sums and percentages.

To commit to a detailed analyses in Phase II, this can only be done with the proviso that the approach may change based on the data distribution, central measures and variation, and particularly time course, the determination of which is a goal of this Phase I trial.

For comparison of change in anxiety and pain from start to end of the waiting room time we propose t-test if normally distributed or the Mann-Whitney U test in the case of non-normal data.

For the time course assessment of pain and anxiety during the procedure there are options depending on whether the data meet the assumptions required for time course analysis.

Descriptive statistics (means and standard deviations as well as counts and percentages) will be calculated for each outcome stratified by time point and by

treatment group. Pain and anxiety trends over time will be assessed graphically for each patient stratified by treatment group.

With the provision that the analysis plan will be adapted based on the metrics found in Phase I, the plan is to follow a previously described path (24):

If the relationship between pain/anxiety is linear over time, and if needed, normality and homoscedasticity of residuals can be achieved by log-transformation, a repeated-measures analysis to compare the effect of treatment, time, and treatment by time interaction on pain and anxiety responses to characterize and compare trends in pain and anxiety ratings for the two treatment conditions over time (66, 67). The analysis will use the reports from the successive 10 min (+/- 2 mins) intervals queries obtained from all patients.

It may be that residuals are neither normally distributed nor possible to obtain a normal distribution by transformation. This happened in prior large scale trial with procedural pain procedural were 47% of pain responses were zero (45). To accommodate such a strong skew in reported pain, we would change our statistical approach to ordinal regression (68). If the proportional odds assumption is met, ordinal regression accounting for repeated measures will be performed to compare the effect of treatment, time, and interaction of treatment by time on pain and anxiety responses. The results will be presented in terms of the slopes of the time course of pain and anxiety on the logit scale.

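### Procedure type is neither stratified nor in the during-treatment analyses, so the average-level and AUC comparisons of pain and anxiety give up precision that a prespecified covariate would recover

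*Combined protocol and SAP*

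**What the plan says.** The Précis (Sample Size and Population) admits patients for bite-appliance and sleep-apnea appliance work as well as "trigger point therapy, botulinum toxin therapy, and various craniofacial and cervical nerve blocks for pain management". The same section describes blocks of four over four tablets. Neither it nor section 3 (item 7), section 4.3 or section 9.2 names a stratification factor.

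Section 9.6 gives three routes for pain and anxiety during treatment:

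- **Repeated measures:** "a repeated-measures analysis to compare the effect of treatment, time, and treatment by time interaction on pain and anxiety responses".
- **Ordinal regression with repeated measures:** the same three terms, used if residuals cannot be made normal.
- **Area under the curve per patient:** compared by t-test or Mann-Whitney, used if neither model fits.

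No route contains procedure type or any other baseline covariate. Later in the section, "Patients' age, gender, procedure type, and NIDA Quick score will be assessed for their potential as confounding factors", and the next sentence gives Phase II design guidance as the purpose. No method, threshold or adjusted pilot estimate is described.

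**The concern.** What is done in the chair may well affect how much pain or anxiety a patient reports there. The appointment is already scheduled when the patient is randomized, so the scheduled procedure is a legitimate baseline covariate. Left out of the model, any level difference between procedures goes into the error term. With 36 patients per arm and no stratification, the arms can also differ visibly in procedure mix by chance.

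Pain and anxiety during treatment are listed secondary outcomes, tested two-sided at the 5% level, and the pilot is meant to supply estimates for Phase II. A more precise estimate of the average effect, together with a residual standard deviation after allowing for procedure, would serve that purpose at almost no cost.

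**Working it through.** **1. The plan's own figures.** No sample size is stated for the during-treatment outcomes. The nearest yardstick is waiting-room anxiety: "Assuming an average anxiety rating of 4 at the end of the waiting room time", "a 35% reduction in anxiety to 2.6", and "a standard deviation of 2, 66 patients would be needed for a two-sided test with a power of 0.80 and an alpha of 0.05". With a difference of 4 − 2.6 = 1.4:

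n per arm = 2 × [(1.960 + 0.842) × 2 / 1.4]² = 32.04, rounded up to 33, so 66 in total. This reproduces the plan's figure. The day-1 pain figure also reproduces: a difference of 3.5 − 1.6 = 1.9 with SD 2.0 needs 18.4 per arm by the t-based formula, rounded up to 19, so 38 in total. I borrow SD 2 below and treat the during-treatment outcome as one level score per patient.

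**2. Precision of a level comparison.** Let R² be the share of outcome variance explained by procedure class. The documents do not give it, so 10% to 40% is an assumed range.

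SE = 2 × √(1 − R²) × √(2/36)

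| R² | SE of difference | Reduction in SE | Difference detectable with 80% power | Power for a 1.0-point difference (illustrative) |
|---|---|---|---|---|
| 0 | 0.471 | – | 1.32 | 56% |
| 0.10 | 0.447 | 5% | 1.25 | 61% |
| 0.20 | 0.422 | 11% | 1.18 | 66% |
| 0.30 | 0.394 | 16% | 1.10 | 72% |
| 0.40 | 0.365 | 23% | 1.02 | 78% |

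For two procedure classes with share p in one of them and a level gap g, R² = p(1 − p)g²/2². At p = 0.5, R² of 10% to 40% corresponds to g = √1.6 = 1.3 to √6.4 = 2.5 points. These figures are for a linear scale and do not carry over directly to the logit scale of the ordinal model.

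**3. Chance imbalance.** The split of a procedure class over 36 and 36 is hypergeometric. The class sizes are assumed. Each is an even number, so the gap between arms must be even too.

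| Class size of 72 (assumed) | Gap of 4 or more visits | Gap of 8 or more visits |
|---|---|---|
| 14 | 37% | 4% |
| 22 | 44% | 7% |
| 36 | 48% | 10% |

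If the class scores 2 points higher (assumed), a 4-visit gap shifts the unadjusted difference by 4/36 × 2 = 0.22 and an 8-visit gap by 8/36 × 2 = 0.44. The unadjusted SE is 0.471.

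**4. The slope comparison.** A procedure main effect adds a constant to all of a patient's readings, so it moves intercepts and leaves within-patient trends alone. A simulation with 72 patients, five readings each, a 2-point level gap and assumed variance components agrees. Adding the main effect lowered the SE of the treatment main effect from 0.42 to 0.35. The treatment-by-time estimate did not change, and its SE went only from 0.088 to 0.087.

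**5. The AUC fallback.** AUC is a level measure, it is unadjusted, and no standardization for chair time is stated. If procedures differ in length as well as level, both differences enter the area. This is the most exposed of the three routes.

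**The case against.** Several counter-arguments have force.

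- **The plan emphasizes trends.** Section 9.6 compares trends over time and reports ordinal results as slopes. Section 2.2 says that in earlier trials the steepness of the pain curve was similar across three very different procedures. This stands for slopes, as step 4 confirms. It does not cover pain level, anxiety level or AUC.
- **The analyses are provisional and secondary.** Section 9.6 says the plan will be adapted to Phase I findings, and the primary outcome is pass/fail feasibility. This stands and limits the importance of the point.
- **The size is assumed.** Procedure mix, level gap and R² are not in the documents. Nor do they show that procedure is the most useful covariate; baseline pain and anxiety are measured and are also absent from the models. This stands.
- **Availability is inferred.** Section 9.6 implies that procedure type is known, but neither the baseline list in section 6.2.2 nor the chairside list in section 6.2.5 names it.

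A reader might infer three stronger points that the documents do not support. The first is that the treatment comparison is confounded. Allocation is randomized, so any imbalance is chance, and the unadjusted standard error already allows for it. The second is that the pilot estimate will be adjusted for covariates picked from the data. The plan describes no such step, only a look intended to inform Phase II. The third is that Phase II sizing is compromised. Its primary outcome is waiting-room anxiety, measured before treatment begins, and an unadjusted SD would size a trial conservatively.

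**Conclusion.** The concern holds for level contrasts only. The design does not balance procedure type, and no during-treatment analysis uses it. If it predicts pain or anxiety level, the average treatment effect and the AUC comparison have a standard error that adjustment would lower by about 5% to 23%, for an assumed R² of 10% to 40% and SD 2 borrowed from the waiting-room calculation. Chance gaps of 4 or more visits between arms would occur in 37% to 48% of allocations under the assumed class sizes.

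The tests remain valid without the covariate. The slope contrast, the feasibility criteria, the waiting-room analysis and the stated sample sizes do not change. This is a low-cost improvement to secondary analyses.

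**What to change.** In section 9.6:

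- Prespecify scheduled procedure class as a fixed effect in the repeated-measures and ordinal models for pain and anxiety during treatment. The clinical investigators should define a small number of classes, and the grouping should be fixed before unblinding.
- Replace the unadjusted AUC test with a linear model adjusted for the same class, or a rank-based analysis of covariance if the data are not normal.
- Add a procedure-by-time term only if a more precise slope is the aim.
- Keep the look at age, gender and NIDA score as descriptive input to Phase II.

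The cost is a few sentences and one or two degrees of freedom, with no extra patients or visits. Before adopting it, confirm that the case report form captures the procedure as scheduled, since a procedure changed after randomization would no longer be a baseline covariate.
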